## **ETHICAL PROCEDURES**

This research will comply with applicable ethical principles throughout its course.

Regarding the principles of beneficence and non-maleficence, it is considered that patients undergoing the intervention will experience health gains and therefore the study will “do good for the participant” (Nunes, 2020) and will not cause harm.

The principle of veracity will also be ensured by informing patients about the risks and benefits of their participation, as stated in the informed consent provided in advance.

Confidentiality will be guaranteed by protecting any personal information collected, ensuring that such data will only be known to the principal investigator and will be deleted upon completion of the research.

Under these principles, participants’ rights will be safeguarded, including: the right to avoid harm, the right to full knowledge about the study, the right to self-determination, the right to anonymity and confidentiality (Nunes, 2020).

The study will be approved by the Ethics Committee of Diaverum – Investimentos e Serviços, Lda., where it will be conducted. Authorization will also be obtained from the clinical directors and nurse managers of the participating units.

Use of the Scale for Assessment of Self-Care Behaviours with AVF in HD has been authorized by its authors.

All paper documentation will be stored in a restricted-access location accessible only to the principal investigator. After data entry into a database and pseudonymization, paper

questionnaires will be destroyed. Digital files will be stored in a password-protected folder accessible only to the principal investigator and supervisor.

All paper and digital files will be destroyed when the study ends.

## **DATA ANALYSIS**

Data analysis will be organized in two parts:

Part 1 – Sociodemographic and clinical variables:

- Mean and median for quantitative variables (age);
- Absolute frequencies and percentages for categorical variables.

Part 2 – Scale results:

- Results presented as percentage of responses, as recommended by the scale's author.

Impact assessment:

Inferential statistics will be used to compare VA self-care behaviours between the two data collection moments (pre- and post-intervention).

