#### A5. STUDY DESIGN

Prospective, quantitative, cross-sectional study, employing a quasi-experimental methodology that involves an initial diagnostic assessment, a subsequent educational intervention to promote adherence to self-care, and an evaluation of outcomes after this intervention.

“Quasi-experimental studies fall within a positivist methodology, as they have a quantitative nature. The way in which the researcher controls the groups exposed to the study and the

manner in which interventions are carried out lead to expected outcomes, that is, an induction of results" (Soares, 2021).

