## METHODS

Study type: Prospective, cross-sectional, quantitative study aimed at evaluating the effectiveness of nursing educational intervention on VA self-care. This study follows a quasi-experimental methodology, involving an initial diagnostic assessment, a set of health education sessions, and a subsequent evaluation of the results of this educational intervention.

Population and sample: The population will consist of individuals with CKD undergoing outpatient HD at two HD units in the central region of Portugal. The sample will be non-probabilistic and selected by convenience, including CKD patients in HD whose VA in use is an AVF, from the two aforementioned HD units.

Inclusion criteria:

- Individuals with CKD in HD;
- Independent in self-care;
- With VA – AVF.

Exclusion criteria:

- VA via CVC or AVG;
- Cognitive impairment (assessed using the Mini Mental State Examination – MMSE – developed by Folstein et al., 1975);
- Lack of fluency in Portuguese.

Data collection instrument: The study will use a data collection instrument consisting of three parts: sociodemographic characterization, clinical characterization of participants, and assessment of AVF self-care behaviours.

The first two parts will include:

- Sociodemographic variables: age (years), sex (male/female), household composition (number of members), education level (illiterate, primary, secondary,

higher education), and employment status (employed, unemployed, homemaker). Categorical variables will be assessed through closed-ended questions, and age will be a continuous variable (years).

- Clinical variables: CKD etiology (diabetes, hypertension, polycystic kidney disease, glomerulonephritis, hypoplasia/dysplasia, unknown, or other causes), HD duration (years), duration of HD with AVF, AVF location/type (cubitocubital, radiocephalic, humerobasilic, humerocephalic, humerohumeral), and previous VA complications (thrombosis and infection episodes). Clinical data will be obtained from patient medical records.

Self-care behaviours will be assessed using the **Scale for Assessment of Self-Care Behaviours with AVF in HD** developed by Sousa et al. (2015), consisting of 16 items, structured into two dimensions:

1. *Prevention of complications* – 10 items assessing behaviours related to preventing AV thrombosis and infection;
2. *Management of signs and symptoms* – 6 items assessing self-care behaviours related to detecting VA complications.

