In its original study, this scale showed good reliability (Cronbach's alpha: global 0.80; prevention subscale 0.72; management subscale 0.80).

A pilot test will be conducted with 4 patients to assess applicability, clarity, and completion time.

Data collection procedure: Participants will be recruited by designated study liaisons from each HD unit, in close collaboration with the principal investigator, according to inclusion/exclusion criteria. Eligible patients will be invited to participate and given full study information. Those who agree will provide written informed consent.

First phase: sociodemographic and clinical data collection and administration of the AVF self-care scale. Data will be collected by the principal investigator, in person, with manual completion of the scale. Duration: ~1 month.

Intervention phase: Based on the first assessment results, patients with suboptimal behaviours will receive a tailored nursing educational intervention—a series of health education sessions integrated into HD sessions—each lasting approximately 30 minutes.

Second phase: Three months later, the scale will be re-administered to all initial participants, regardless of the need for intervention. Data collection will again be by the principal investigator, in person, with manual completion. Duration: ~1 month.

Each participant will be assigned an alphanumeric code for pairing pre- and post-intervention data. The code–name key will be accessible only to the principal investigator.

Nursing educational intervention: A set of individual health education sessions, delivered using expository methods and an informational leaflet, focusing on:

- Prevention of thrombosis and infection (recognition of complications during and between HD sessions, hemostasis care, limb protection from trauma, avoidance of non-HD punctures);
- Correct assessment of signs/symptoms suggestive of AVF complications (AVF functionality assessment via thrill palpation, detection of thrombosis by absence of thrill, changes in colour/sensation of the limb, limb pain).

The sessions will be conducted by the principal investigator.

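### Does the plan compare response percentages between the two moments and so throw away each patient's paired score?

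*Combined protocol and SAP*

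**What the plan says.** Four parts of the combined protocol and SAP bear on this.

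- **Design label.** A5. STUDY DESIGN reads "Prospective, quantitative, cross-sectional study, employing a quasi-experimental methodology". METHODS, under study type, repeats the label: "Prospective, cross-sectional, quantitative study aimed at evaluating the effectiveness of nursing educational intervention on VA self-care".
- **Measurement scheme.** METHODS, data collection procedure, states that three months later "the scale will be re-administered to all initial participants, regardless of the need for intervention". It adds: "Each participant will be assigned an alphanumeric code for pairing pre- and post-intervention data".
- **Instrument.** METHODS describes the scale as "consisting of 16 items, structured into two dimensions", with 10 items on preventing complications and 6 on managing signs and symptoms. No scoring rule is given.
- **Analysis.** DATA ANALYSIS, Part 2, says "Results presented as percentage of responses" and attributes this format to the scale's author. Under the separate heading Impact assessment it says only: "Inferential statistics will be used to compare VA self-care behaviours between the two data collection moments (pre- and post-intervention". It names no score, test, unit of analysis or significance level.

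**The concern.** A cross-sectional study has no second measurement to pair, and a percentage taken over all answers at one moment belongs to no single patient. Read together, the label and the reporting format suggest a comparison of two sets of percentages as if they came from different people.

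Three faulty analyses could follow:

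- An unpaired test on paired data would be too conservative and would lose power.
- Pooling all answers would treat 16 correlated responses from one patient as independent.
- Testing each item separately would give 16 tests with none designated primary.

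The pre-post comparison answers the study's second objective, so an error here would affect the main result.

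**Working it through.** The documents give no sample size, significance level, effect size, standard deviation or pre-post correlation, so there is no stated figure to reproduce. The check is first of the text and then of the magnitudes that the concern would need.

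**1. Is the percentage the variable to be tested?** Part 2 concerns how scale results are presented. Impact assessment is a separate heading, and what it compares is self-care behaviours between the two moments. It does not refer back to the percentages. Making the Part 2 format the test variable is an inference that the text does not make.

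**2. Is the pairing discarded?** The only statement about linkage is in METHODS, and it provides a code whose stated purpose is pairing. The same people are measured at both moments. DATA ANALYSIS does not repeat this, but its silence is not an instruction to drop it.

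**3. Does a percentage rule out pairing?** No. Each item answer belongs to a coded patient. A percentage at two moments can be compared within patients with McNemar's test or a test of marginal homogeneity. The wording may also mean a percentage score for each patient, which can be paired directly. The documents do not settle which is meant.

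**4. Does the label alter the analysis?** A5 and METHODS both go on to describe an initial assessment, an educational intervention and a later evaluation. The label is wrong for that design, but no formula or procedure depends on it.

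**5. How large would the errors be if those analyses were done?** Assume n = 60, a two-sided 5% test and equal variances. None of these comes from the documents.

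*Unpaired instead of paired.* For a change of d SD and correlation r, the paired test has noncentrality d/√(2(1 − r)) × √60. The unpaired statistic on the same data has mean d/√(2/60) and variance about 1 − r.

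| d | r | Paired power | Unpaired power |
|---|---|---|---|
| 0.3 | 0.3 | 49% | 34% |
| 0.3 | 0.6 | 72% | 30% |
| 0.3 | 0.7 | 84% | 27% |
| 0.5 | 0.6 | 99% | 88% |

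The loss runs from modest to severe, depending on assumptions that cannot be checked here.

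*Pooled answers.* METHODS reports a global Cronbach's alpha of 0.80. Over 16 items this implies a mean inter-item correlation of 0.80/(16 − 0.80 × 15) = 0.20 and a design effect of 1 + 15 × 0.20 = 4.0. By a simple approximation, the true size is 2(1 − Φ(1.96/√(4.0 × (1 − r)))). This gives 24% at r = 0.3, 12% at r = 0.6, 5.0% at r = 0.75 and 2.8% at r = 0.8. The direction of the error reverses as r rises, so an excess of false positives is not a general result.

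*Sixteen item tests.* With independent tests, 1 − 0.95^16 = 56%. That counts rejections in either direction, including chance worsening. For a chance improvement the figure is 1 − 0.975^16 = 33%. Positive correlation between the item tests lowers both: with correlation 0.20, simulation gives about 52% and 27%. A chance improvement is therefore not more likely than not.

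**The case for a change.** The strongest opposing argument is that DATA ANALYSIS is the whole analysis plan and leaves the main comparison open. It has no scoring rule, no primary variable among the 16 items, two dimensions and a global score, no named test, and no statement that the pairing code enters the test. A code is a data-management step and does not define an analysis. With a cross-sectional label and percentages as the only stated summary, an unpaired comparison of percentages is a possible reading, and the choice of score could be made after the data are seen.

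The gaps are real. Naming the score and a paired test in advance would improve the plan, and the label should be corrected. But these are omissions. They do not show that a wrong analysis has been specified, and a paired analysis of a patient-level score fits the text at least as well. The unpaired, pooled and item-by-item analyses are three alternative guesses, and the plan commits to none of them. An analyst holding coded, paired data would be expected to use the pairing.

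**Conclusion.** The concern does not hold. No passage says that the impact comparison runs on response percentages in place of paired patient scores. The percentage sentence governs presentation, the comparison is left unspecified, and the one statement on linkage provides for pairing.

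No error of a definite size can be attached to the plan. The power losses, inflated error rates and multiplicity figures each require an analysis that the documents do not state, together with an assumed sample size, effect or correlation (or, for the item tests, independence). Two minor points remain: a cross-sectional label that does not fit a two-moment design and changes no calculation, and missing detail on the score and the paired test. This conclusion rests on the reading that silence in DATA ANALYSIS does not override the pairing provided for in METHODS.

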**TIMELINE:**

Activities	04/2024	05/2024	06/2024	07/2024	08/2024	09/2024	10/2024	11/2024	12/2024	01/2025	02/2025	03/2025	04/2025	05/2025
Literature Review														
Participant identification														
Data Collection (moment 1)														
Data analysis														
Intervention preparation														
Intervention														
Data Collection (moment 2)														
Data analysis														
Interpretative results analysis														
Final report and submission														

## EXPECTED RESULTS

At a higher level of abstraction, the primary expected outcome of this study is an improvement in VA self-care capacity among CKD outpatients undergoing HD.

It is also relevant to reflect on possible health gains for patients and contributions to nursing professional development.

From the analysis of behaviours related to AVF complication prevention and management, it is expected that patients will demonstrate knowledge of the necessary self-care behaviours to recognize changes in AVF function and to adopt behaviours that prevent and/or detect complication signs.

It is considered essential to implement health education programs promoting VA self-care behaviours, as Sousa et al. (2020) observed that patients targeted by structured nursing interventions show better general self-care behaviours and improved AVF maintenance practices.

Nursing practice in the follow-up and monitoring of CKD patients on regular HD is extremely important. In addition to providing treatment-specific care, the nurse should establish a therapeutic relationship with the patient. One of this study's objectives is to empower patients for self-care and promote their involvement in treatment, negotiating and adapting strategies, facilitating the transition process, and fostering self-care—always aiming to address real patient needs.

Developing nursing care conceptualization that ensures high-quality standards is essential for professional practice, representing another expected result and, ultimately, this project's contribution to nursing practice in CKD patient care.

## C. BUDGET

Not applicable.

## E. DISCLOSURE OF INTEREST

This research project was developed within the Curricular Unit “Internship in Nursing for the Person with Chronic Conditions” (1st year, 2nd semester) of the Master’s Degree in Medical-Surgical Nursing (MEMC) – chronic condition area – at the School of Health Sciences of Aveiro (ESSUA) during the 2023–2024 academic year, under the supervision of [name] [name].

The research will be conducted in the 3rd semester of the MEMC – chronic condition area – and will be disseminated at ESSUA, in the participating centres, and at relevant congresses in Medical-Surgical Nursing and Nephrology. Publication in scientific journals in the field is also intended.
